4.6.2. Benefit Assessment

In subjects with T2DM treatment with albiglutide lyophilized drug product resulted in clinically relevant lowering of HbA_{1c} at both the 30 mg and 50 mg doses when given as monotherapy and in combination with metformin, sulfonylureas (SUs), thiazolidinedione or basal insulin. The durability of the effect on glycemic control was shown over a study period of up to 3 years. Consistent with its mechanism of action, albiglutide was not associated with clinically relevant hypoglycemia except when used in combination with an SU or insulin, and incidence rates with the combination were less than those reported with SUs or insulin alone. Body weight decreased slightly or remained stable during treatment, which is of benefit considering that continuous weight gain is a clinical problem in this patient group. Maintaining body weight while decreasing HbA_{1c} is therefore considered a beneficial effect of importance.

There are no clinical data available for the use of the albiglutide liquid drug product in humans. Based on the understanding of albiglutide degradation pathways and clinical outcomes from exposure to variants/impurities clinical comparability between the liquid drug product and lyophilized drug products is expected.

4.6.3. Overall Benefit: Risk Conclusion

Taking into account the measures taken to minimize risk to subjects participating in this study, the known and potential risks identified with albiglutide are justified by the benefits demonstrated in subjects with T2DM.

5. SELECTION OF STUDY POPULATION AND WITHDRAWAL CRITERIA

Specific information regarding warnings, precautions, contraindications, AEs, and other pertinent information on the GSK investigational product or other study treatment that may impact subject eligibility is provided in the IB and in the product labeling for those countries where marketing authorization for the albiglutide lyophilized DCC pen injector has been granted.

Deviations from inclusion and exclusion criteria are not allowed because they can potentially jeopardize the scientific integrity of the study, regulatory acceptability or subject safety. Therefore, adherence to the criteria as specified in the protocol is essential.

5.1. Inclusion Criteria

A subject will be eligible for inclusion in this study only if all of the following criteria apply:

[1] AGE

- | |
|---|
| 1. Aged 18 to 80 years of age inclusive, at the time of signing the informed consent. |
|---|

[2] TYPE OF SUBJECT AND DIAGNOSIS INCLUDING DISEASE SEVERITY
--

- | |
|---|
| 2. Historical diagnosis of T2DM (at least 3 months), experiencing inadequate glycemic control on current regimen of diet and exercise or on a stable dose of metformin of at least 1500 mg or the documented maximal tolerated dose if less than 1500 mg metformin (monotherapy), maintained for approximately 8 weeks prior to screening |
| 3. HbA _{1c} $\geq 7.0\%$ and $\leq 10\%$. If the first screening HbA _{1c} does not meet the eligibility criterion, the HbA _{1c} value may be checked up to 2 times during screening, and if the average of these determinations meets the criterion, the subject can be randomly assigned to treatment. |
| 4. Hemoglobin ≥ 11 g/dL (≥ 110 g/L) for males and ≥ 10 g/dL (≥ 100 g/L) for females. |

[3] WEIGHT

- | |
|--|
| 5. Body mass index ≤ 40 kg/m ² . |
|--|

[4] SEX

- | |
|--|
| 6. Male or female |
| 7. Female subject is eligible to participate if she is not pregnant (as confirmed by a negative serum human chorionic gonadotrophin (hCG) test for females of reproductive potential only), not breastfeeding, and at least one of the following |

conditions applies:

- a) Reproductive potential and agrees to follow one of the options listed in the GSK Modified List of Highly Effective Methods for Avoiding Pregnancy in Females of Reproductive Potential (FRP) (eg., combined oral contraceptive pill; see [Appendix 2](#)) from 30 days prior to the first dose of study medication and until after the last dose of study medication and completion of the follow-up visit.
 - This does not apply to FRP with same sex partners, when this is their preferred and usual lifestyle or for subjects who are and will continue to be abstinent. Other situations in which contraception in FRP may not need to be mandated should be discussed with the Medical Monitor.
- b) Non-reproductive potential defined as either:
 - Pre-menopausal with one of the following: (i) documented tubal ligation; (ii) documented hysteroscopic tubal occlusion procedure with follow-up confirmation of bilateral tubal occlusion; (iii) hysterectomy; or (iv) documented bilateral oophorectomy, or;
 - Postmenopausal defined as 12 months of spontaneous amenorrhea and age appropriate (i.e., >50 years). In questionable cases, a blood sample with simultaneous follicle stimulating hormone (FSH) >40 mIU/mL and estradiol <40 pg/mL (<140 pmol/L) is confirmatory, depending on local laboratory ranges. Females on hormone replacement therapy (HRT) and whose menopausal status is in doubt will be required to use one of the highly effective contraception methods if they wish to continue their HRT during the study. Otherwise, they must discontinue HRT to allow confirmation of post-menopausal status prior to study enrolment.

[5] INFORMED CONSENT

8. Able and willing to provide informed consent.

5.2. Exclusion Criteria

A subject will not be eligible for inclusion in this study if any of the following criteria apply:

[1] CONCURRENT CONDITIONS/MEDICAL HISTORY (INCLUDES LIVER FUNCTION AND QTc INTERVAL)

1. Type 1 diabetes mellitus
2. History of cancer that has not been in full remission for at least 3 years before screening. (A history of squamous cell or basal cell carcinoma of the skin or treated cervical intra-epithelial neoplasia I or II is allowed).
3. Personal or family history of medullary thyroid carcinoma or multiple endocrine neoplasia type 2.
4. History of acute or chronic pancreatitis.
5. Abnormal (i.e., outside the normal reference range) thyroid stimulating hormone

(TSH) at screening.

6. Severe gastroparesis, i.e., requiring regular therapy within 6 months before screening.
7. History of significant GI surgery that in the opinion of the investigator is likely to significantly affect upper GI or pancreatic function (e.g., gastric bypass and banding, antrectomy, Roux-en-Y bypass, gastric vagotomy, small bowel resection, or surgeries thought to significantly affect upper GI function).
8. History of severe hypoglycemia unawareness (i.e., the absence of autonomic warning symptoms before the development of neuroglycopenic symptoms such as blurred vision, difficulty speaking, feeling faint, difficulty thinking, and confusion)..
9. Diabetic complications (e.g., active proliferative retinopathy or severe diabetic neuropathy) or any other clinically significant abnormality (including a psychiatric disorder) that, in the opinion of the investigator, may pose additional risk in administering the investigational product.
10. Clinically significant CV and/or cerebrovascular disease within 3 months before screening including, but not limited to, the following:
 - Stroke or transient ischemic attack.
 - Acute coronary syndrome (MI or unstable angina not responsive to nitroglycerin).
 - Cardiac surgery or percutaneous coronary procedure.
 - Current or history of heart failure (New York Heart Association class III or IV).
11. QTcF > 470 msec, where QTcF is the QT interval corrected for heart rate according to Fridericia's formula.
12. ALT >2.5xULN or bilirubin >1.5xULN (isolated bilirubin >1.5xULN is acceptable if bilirubin is fractionated and direct bilirubin <35%).
13. Current active liver or biliary disease (with the exception of Gilbert's syndrome or asymptomatic gallstones or otherwise stable chronic liver disease per investigator assessment).

NOTES:

- Stable chronic liver disease should generally be defined by the absence of ascites, encephalopathy, coagulopathy, hypoalbuminaemia, oesophageal or gastric varices, or persistent jaundice, or cirrhosis.
 - Chronic stable hepatitis B and C (e.g., presence of hepatitis B surface antigen (HBsAg) or positive hepatitis C antibody test result at screening or within 3 months prior to first dose of study treatment) are acceptable if subject otherwise meets entry criteria.
14. eGFR ≤ 30 mL/min/1.73 m² (calculated using the MDRD formula) at screening.

Note: The use of metformin in subjects with varying degrees of renal function should be in accordance with the metformin product label.

15. Hemoglobinopathy that may affect proper interpretation of HbA_{1c}.
16. Medical or psychiatric disorders that would preclude effective participation in study.

[2] CONCOMITANT MEDICATIONS (see Section 6.10)

17. Use of oral or systemically injected glucocorticoids within the 3 months before randomization or high likelihood of a requirement for prolonged treatment (>1 week) in the 6 months following randomization. However, short courses of oral steroids (single dose or multiple doses for up to 7 days) may be permitted provided these cases are discussed with the medical monitor. Inhaled, intra-articular, epidural, and topical corticosteroids are allowed.
18. Use of GLP 1 receptor agonists at any time. Use of dipeptidyl peptidase-IV inhibitors within the 3 months before randomization. Use of any other antidiabetic medications with the exception of metformin within 3 weeks before randomization.

[3] RELEVANT HABITS

19. History of alcohol or substance abuse within one year before screening.

[4] CONTRAINDICATIONS

20. Known allergy to albiglutide or any product components (including yeast and human albumin), any other GLP-1 analogue, or other study medication's excipients OR other contraindications (per the prescribing information) for the use of potential study medications.

[5] DIAGNOSTIC ASSESSMENTS AND OTHER CRITERIA

21. Positive urine alcohol/drug screen result at Screening, unless the subject is taking a medically approved medication for which a positive drug screen simply verifies the use of this medication
22. A positive test for human immunodeficiency virus (HIV) antibody.
23. The subject has participated in a clinical trial and has received an investigational product within the following time period prior to the first dosing day in the current study: 30 days, 5 half-lives or twice the duration of the biological effect of the investigational product (whichever is longer).
24. Fasting triglyceride level >750 mg/dL at screening.

5.3. Screening/Baseline/Run-in Failures

Screen failures are defined as subjects who consent to participate in the clinical trial but are never subsequently randomized. In order to ensure transparent reporting of screen failure subjects, meet the Consolidated Standards of Reporting Trials (CONSORT) publishing requirements, and respond to queries from regulatory authorities, a minimal set of screen failure information is required including demography, screen failure details, eligibility criteria, and any SAEs.

- Re-screening of subjects who did not meet the eligibility criteria for HbA_{1c} ($\geq 7.0\%$ and $\leq 10\%$) is permitted. If the first screening HbA_{1c} does not meet the eligibility criterion, the HbA_{1c} value may be checked two further times during the screening period, and if the average of these determinations meets the entry criterion, the subject can be randomized.

5.4. Hyperglycemia Rescue

During the study of diabetics, there is always the possibility of hyperglycemia, which might impact subject safety. After randomization, subjects who experience persistent hyperglycemia will qualify to undergo hyperglycemia rescue. Investigators must adhere to the labeling of the US FDA-approved prescribing information or to the local labeling of the respective country for all rescue medications. The conditions for hyperglycemia rescue are defined in [Table 3](#).

Table 3 Conditions for Hyperglycemia Rescue

Time Interval on Treatment	Hyperglycemia Rescue
\geq Day 1 and $<$ Week 2	No rescue
\geq Week 2 and $<$ Week 4	FPG ≥ 280 mg/dL ¹
\geq Week 4 and $<$ Week 12	FPG ≥ 250 mg/dL ¹
\geq Week 12 and $<$ Week 26	HbA _{1c} $\geq 8.5\%$ and $\leq 0.5\%$ reduction from Baseline

1. Confirmed by a second sample drawn within 7 days analyzed by the central laboratory

Subjects can be rescued at any time on or after Week 2. Subjects who qualify should return to the study center at the next scheduled weekly visit for rescue. The efficacy assessments should be obtained if these assessments are not included as part of the regular scheduled visit. As determined by the investigator, rescued subjects may be seen more frequently during unscheduled visits until their diabetes has stabilized. Subjects will continue in the study after rescue and will continue with their blinded study treatment until the study is completed. It is critical that subjects continue in the study after rescue in order to have complete and unbiased follow-up of long-term safety and efficacy assessments.

The rescue criteria above should apply in the majority of circumstances; however, in the event a subject experiences significant evidence of hyperglycemia (e.g., symptoms of polyuria and polydipsia and laboratory evidence of hyperglycemia), the investigator may, based upon his or her judgment, rescue the subject with appropriate therapy at any time following randomization. Such subjects may either have rescue medication added to the

existing randomly assigned study medication or, if in the judgment of the investigator (or the product labeling for rescue medications) this is not appropriate, the subject will be discontinued from randomly assigned study medication and appropriate rescue therapy initiated. Such subjects will continue to be followed in the study for their safety information; however, they will not receive further randomly assigned study medication. Rather they will be prescribed alternative therapy in order to optimize their diabetes control.

The preferred postrescue add-on treatment is insulin. Other medications may be added at the investigator's discretion. The addition of other GLP-1 analogues (exenatide or liraglutide) is prohibited as the safety of dosing with multiple GLP-1 analogues is unknown. The use of dipeptidyl peptidase-IV inhibitors is prohibited. The addition of a thiazolidinedione (rosiglitazone or pioglitazone) is discouraged.

5.5. Withdrawal/Stopping Criteria

Every effort should be made to keep subjects in the study. The reason for a subject discontinuing investigational product or withdrawing from the study will be recorded in the subject's electronic case report form (eCRF).

5.5.1. Permanent Discontinuation of Investigational Product

A subject may permanently discontinue investigational product at any time at his/her own request, or at the discretion of the investigator for safety or compliance reasons. A subject must permanently discontinue investigational product for the pre-specified reasons below.

- Any AE, which, in the opinion of the investigator precludes effective participation of the subject or poses a safety concern
- The following AEs **will** require discontinuation from investigational product:
 - Confirmed pancreatitis, acute or chronic.
 - Pancreatic cancer.
 - Confirmed MTC or other thyroid C-cell neoplasia.
 - Liver chemistry abnormalities exceeding the threshold criteria outlined in Section [5.5.4](#)
 - QTc abnormalities exceeding the threshold criteria outlined in Section [5.5.5](#).
 - Severe allergic/hypersensitivity reactions that are considered by the investigator to be attributable to investigational product or without a likely alternative aetiology.
- $eGFR \leq 30 \text{ mL/min/1.73 m}^2$ (calculated using the MDRD formula).
- Subject becomes pregnant or intends to become pregnant during the study.
- Need for chronic use of a prohibited concomitant medication (Section [6.10.2](#))

- Major protocol deviation (the investigator should discuss the protocol deviation with the medical monitor before withdrawing study medication)
- Subject decision (reason to be documented in the eCRF, if specified by the subject)
- Investigator discretion
- Study closed/terminated or investigator site closed (where subject transfer to another site is not possible)

In all cases, the reasons for investigational product discontinuation and the date of the last dose will be recorded in the subject's electronic case report form (eCRF) and the subject will continue in the study as described in [5.5.1](#)

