7.4.1.5. AEs of Special Interest

In the Phase IIIa clinical development program, AEs of special interest included several areas of safety related concern for the T2DM population, particularly for a GLP-1R agonist such as albiglutide.

Specific eCRF pages will be used to capture additional details for the following AEs of special interest:

- Hypoglycemic events
- Liver events
- CV events (see Section [7.4.1.4](#))
- Injection site reactions
- Potential systemic allergic reactions
- Pancreatitis
- MTC
- Diabetic retinopathy
- Pneumonia
- Atrial fibrillation/atrial flutter

The following additional AEs of special interest will be captured in the AE eCRF pages:

- GI events
- Pancreatic cancer
- Malignant neoplasms
- Appendicitis

Subjects with drug hypersensitivity reactions that are not reasonably attributable to another cause or pancreatitis should discontinue investigational product and should not be rechallenged with albiglutide (see Section [5.5](#) for complete list of AEs of special interest requiring withdrawal).

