12.5.5. Evaluating AEs and SAEs

Assessment of Intensity

The investigator will make an assessment of intensity for each AE and SAE reported during the study and will assign it to one of the following categories:

- Mild: An event that is easily tolerated by the subject, causing minimal discomfort and not interfering with everyday activities.
- Moderate: An event that is sufficiently discomforting to interfere with normal everyday activities
- Severe: An event that prevents normal everyday activities. - an AE that is assessed as severe will not be confused with an SAE. Severity is a category utilized for rating the intensity of an event; and both AEs and SAEs can be assessed as severe.
- An event is defined as 'serious' when it meets at least one of the pre-defined outcomes as described in the definition of an SAE.

Assessment of Causality

- The investigator is obligated to assess the relationship between study treatment and the occurrence of each AE/SAE.
- A "reasonable possibility" is meant to convey that there are facts/evidence or arguments to suggest a causal relationship, rather than a relationship cannot be ruled out.
- The investigator will use clinical judgment to determine the relationship.
- Alternative causes, such as natural history of the underlying diseases, concomitant therapy, other risk factors, and the temporal relationship of the event to the study treatment will be considered and investigated.
- The investigator will also consult the Investigator Brochure (IB) and/or Product Information, for marketed products, in the determination of his/her assessment.
- For each AE/SAE the investigator **must** document in the medical notes that he/she has reviewed the AE/SAE and has provided an assessment of causality.
- There may be situations when an SAE has occurred and the investigator has minimal information to include in the initial report to GSK. However, **it is very important that the investigator always make an assessment of causality for every event prior to the initial transmission of the SAE data to GSK.**
- The investigator may change his/her opinion of causality in light of follow-up information, amending the SAE data collection tool accordingly.
- The causality assessment is one of the criteria used when determining regulatory reporting requirements.

Follow-up of AEs and SAEs

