7.1.1.1. Primary Analysis on Primary Efficacy Endpoint

The primary endpoint is the change from baseline in HbA_{1c} at Week 26. The primary analysis of the primary endpoint will be conducted using a mixed-effect model with repeated measures (MMRM) in the ITT Population. The primary analysis will include all HbA_{1c} values collected at scheduled visits from Week 4 up to Week 26. This will include values after hyperglycemia rescue and discontinuation from investigational product. Imputation under the non-inferiority null hypothesis for missing data will be incorporated [Koch, 2008]. Multiple imputation assuming missing at random (MAR) will be used to replace missing data of change from baseline of HbA_{1c} at Week 26 for all subjects in both treatment arms as a first step, and then to make all the imputed values for the liquid drug product arm worse by the non-inferiority margin 0.4.

Multiple imputation approach under MAR uses separate means and variance-covariance parameter estimation for each treatment arm (Carpenter and Kenward, 2013). Missing values for each subject will be imputed multiple times based on his or her own observed HbA_{1c} change from baseline values available and also based on the estimated means and variance-covariance from the treatment group where that subject is randomized to. This approach will be used for all missing data at Week 26 due to any reason including, but not limited to lost to follow-up and withdrawal consent. The details of implementing this multiple imputation approach are the following:

- **Step 1a:** Missing values at Week 26 will be imputed 100 times via SAS PROC MI (specifying BY treatment group, using MCMC statement with the option chain = multiple, including baseline and all post-baseline scheduled visits up to Week 26). As a result, 100 imputed datasets will be generated. Note: Only imputed values at Week 26 will be retained while the imputed values at other visits will be dropped from the imputed datasets.
- **Step 1b:** For each of the 100 imputed datasets from Step 1 the imputed values at Week 26 for the liquid drug product arm will be increased by 0.4.
- **Step 2:** Apply MMRM analysis as specified below for each of the 100 imputed dataset and save LSmeans (standard error) for each treatment arm at Week 26 and difference in LSmeans between treatment groups (standard error) from each of the 100 analyses.

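### Protocol 5.5.1 and 7.4.1.5 differ on stopping treatment after a non-severe, otherwise unexplained hypersensitivity reaction that is not judged a safety concern

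*Protocol*

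**What the plan says.** Protocol Section 5.5.1 opens its list with a binding statement: "A subject must permanently discontinue investigational product for the pre-specified reasons below". The hypersensitivity entry in that list is "Severe allergic/hypersensitivity reactions that are considered by the investigator to be attributable to investigational product or without a likely alternative aetiology". The same list begins with a general entry, "Any AE, which, in the opinion of the investigator precludes effective participation of the subject or poses a safety concern", and also includes investigator discretion and subject decision.

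Protocol Section 7.4.1.5, on adverse events of special interest, says: "Subjects with drug hypersensitivity reactions that are not reasonably attributable to another cause or pancreatitis should discontinue investigational product". It adds that such subjects should not be given albiglutide again, and then refers the reader to Section 5.5 "for complete list of AEs of special interest requiring withdrawal".

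Both are current text. Appendix 9 shows that Amendment 2 revised both provisions, replacing withdrawal from the study with discontinuation of the product, and left the difference in severity scope in place. The SAP has no rule of its own for stopping after hypersensitivity.

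**The concern.** The two sections address the same event and set different thresholds. One is confined to severe reactions and the other is not. The broader sentence also cites the narrower list as complete, so a reader who follows the cross-reference finds a rule that does not match the sentence that led there.

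Consistent handling of a named risk is at stake. Dosing is weekly, so a subject who continues after a reaction is exposed again at the next visit. Table 2 in Section 4.6.1 describes a non-serious event with dyspnea on rechallenge, and Section 4.6 says this is the first clinical use of the liquid product in subjects with type 2 diabetes. There is also a compliance question. Section 7 allows no waivers except for immediate safety concerns, yet while both sentences stand a monitor cannot say whether continued dosing after such a reaction is a deviation.

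**Working it through.** No sample size, power or alpha figure is involved, so the main check is a comparison of the texts.

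| Element | Section 5.5.1 | Section 7.4.1.5 |
|---|---|---|
| Force | *must* / *will* | *should* |
| Severity | severe only | no limit |
| Causality test | attributed to the product, or no likely other cause | no other reasonable cause |
| After stopping | permanent | no rechallenge |

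The last row agrees, since permanent discontinuation already rules out rechallenge. The first three rows differ.

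*What severe means.* Section 12.5.5 treats it as an intensity grade: "Severity is a category utilized for rating the intensity of an event; and both AEs and SAEs can be assessed as severe". The word therefore limits the 5.5.1 entry in practice. If it were instead read clinically, as in Section 7.7, which names anaphylaxis and angioedema, the 5.5.1 entry would still be narrower than 7.4.1.5.

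*Applying both sections to a drug hypersensitivity reaction with no other cause:*

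1. Severe: both sections lead to stopping.
2. Not severe, but judged by the investigator to be a safety concern or to preclude effective participation: the first entry in 5.5.1 makes stopping mandatory, and 7.4.1.5 says the subject should stop. The outcome is the same.
3. Not severe and not judged in that way: 7.4.1.5 says the subject should stop. In 5.5.1 the hypersensitivity entry and the safety-concern entry do not apply. The investigator-discretion and subject-decision entries permit stopping without calling for it. The instructions differ.

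The conflict is case 3 only.

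*How often.* The documents give no rate for case 3. An illustration is possible from three inputs: over 4000 subject-years of albiglutide exposure (Section 4.6), one described event consistent with a possible albiglutide-related systemic reaction (Table 2), and about 300 subjects treated for 26 weeks.

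- Exposure in this trial: 300 × 26/52 = 150 subject-years.
- Expected events if that was the only one and the liquid product behaves alike: 150 × 1/4000 = 0.0375, about 0.04.
- At ten times that rate: 0.375, about 0.4.

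Both conditions are assumptions. The event's intensity grade is not given, and the 7.4.1.5 test may also catch milder reactions not counted here. The figures show only that few subjects are likely to be involved.

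*Effect on analyses.* SAP 7.1.1.1 says of the HbA1c values in the primary analysis: "This will include values after hyperglycemia rescue and discontinuation from investigational product". Stopping therefore does not remove a subject's values. Inconsistent stopping could reach supportive analysis 2 (SAP 7.1.1.2), the on-treatment sensitivity analysis (SAP 11.6.3.4), per-protocol membership (SAP 4.1), and the summaries of exposure and of adverse events leading to discontinuation (SAP 6.5 and 8.2.6).

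**The case against.** The strongest defence is that the two rules are nested. Section 5.5.1 sets a mandatory minimum for severe reactions, 7.4.1.5 adds broader advice, and the cross-reference means that 5.5 governs what is compulsory. Neither section tells a site to keep dosing after a non-severe reaction, so a site that stops breaches neither. Section 5.5.1 also has its mandatory entry for any event that the investigator regards as a safety concern.

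Much of this stands. It rules out the reading, which a reader might infer from the severity wording alone, that the sections conflict for every mild or moderate reaction without another cause; case 2 above falls outside the conflict. It does not remove the problem. *Should* can fairly be read as an instruction, and nothing in the text says that it is only advice. The safety-concern entry depends on individual opinion. In case 3 one site can stop and another continue, and both can cite the protocol.

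A second objection is that the statistical consequence is slight, and that is right. The trial is randomized and double-blind, so the same reaction has no reason to be handled differently by arm. Under Protocol 9.4.2 the safety variables have no inferential testing.

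A reader might also infer that uneven stopping adds noise to injection-site reaction counts. The documents do not support this. Injection-site reactions and potential systemic allergic reactions are separate items in 7.4.1.5 and are analyzed separately in SAP 8.2.2 and 8.2.7.6, and neither stopping sentence mentions injection-site reactions.

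**Conclusion.** The point holds as an internal inconsistency with patient-safety relevance. It concerns one class of event: a non-severe drug hypersensitivity reaction with no other explanation that the investigator does not regard as a safety concern or as precluding effective participation. For that class the two sections differ in severity scope and force. Their causality tests are also worded differently, and the claim that 5.5 is complete is not true of the sentence that makes it. No other text in the protocol or SAP reconciles them.

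The size cannot be computed from the documents. On the assumptions stated, the expected number of affected subjects is well below one. With so few subjects, and with post-discontinuation HbA1c retained, the effect on the primary analysis is negligible. The supportive and descriptive analyses named above could be touched only slightly. The case for acting rests on consistent handling of subjects and on being able to classify deviations, not on any threat to the non-inferiority result. Whether the narrower or the broader rule is clinically right is not judged here.

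**What to change.** Reconcile Sections 5.5.1 and 7.4.1.5 so that both state the same severity scope, the same causality test and the same force (*must* or *should*), and so that the reference to 5.5 as a complete list is true. If the difference is intended, with a mandatory rule for some reactions and advice for others, say so in both places. The medical team should choose the rule. The cost is about one sentence in a protocol amendment or a clarification letter to sites. It needs no change to the SAP, the sample size or data collection.
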